3.1 STATISTICAL HYPOTHESES

Not Applicable

3.2 STATISTICAL DECISION RULES

The alpha level will be 0.05, 2-sided. No adjustments for multiple comparisons will be made.

4 ANALYSIS SETS/POPULATIONS

The analysis population will include adolescents and young adults 15 to 30 years of age during 01 January 2016 – 31 December 2021

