9. RESEARCH METHODS

9.1. Study Design

This is a retrospective cohort study using health care administrative claims data as described in Section 9.4 Data Sources.

Adolescents and young adults approximately 15 to 30 years of age at their individual time zero (calculated based on birth year) will be identified from administrative claims during 01 January 2016 and 31 December 2021.

The exposure cohort will be the individuals who have received at least 1 dose of Trumenba and at least 1 dose of MenACWY (Menactra[®], Menveo[®], or MenQuadfi[®]) prior to the Trumenba vaccination, between 01 January 2016 and 31 December 2021. The index date (zero time) for the exposed cohort is the last date of vaccination, and the cohort will be followed from 14 days after vaccination to the end of the study period (31 December 2022). The individuals in the cohort will be censored by the event of interest, death date (if known), plan disenrollment (if known) or the end of the study period, whichever comes first.

PFIZER CONFIDENTIAL CT24-WI-GL02-RF02 4.0 Non-Interventional Study Protocol Template For Secondary Data Collection Study 01-Jun-2022 Page 11 of 22

The reference cohort will be those with at least 1 dose of MenACWY vaccine, but no doses of Trumemba during the observation period, received between 01January 2016 and 31 December 2021. The MenACWY-only vaccinated cohort is used as a reference cohort rather than an unvaccinated cohort in order to help control for theoretical differences in health seeking and risk behaviors between vaccinated and unvaccinated individuals. The index date (zero time) of the reference cohort is the last dose of MenACWY and these individuals will be followed from 14 days after zero time until the earliest occurrence of the following: outcome of interest, death date (if known), plan disenrollment (if known) or 31 December 2022 (end of study period).

The outcomes of interest are gonococcal and chlamydial infections and only the first episode within the study period will be considered as event in case of repeated infections.

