9.2.1. Inclusion Criteria

Patient records must meet all of the following inclusion criteria to be eligible for inclusion in the study:

- 1. Individuals of approximately 15-30 years old (using July 1 of birth year) enrolled in a health plan available in PharMetrics Plus database during 01 January 2016 and 31 December 2021.
- Individuals having at least 1 dose of MenACWY during 01 January 2016 and 31 December 2021.

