2.1 STUDY DESIGN

This is a retrospective cohort study including individuals 15 to 30 years of age enrolled in a health plan covered by IQVIA PharMetrics® Plus during 1 Jan 2016 to until the latest release of the data (October 2022). The study is to estimate the effect of Trumenba vaccination on the disease of interest, in particular, the gonococcal incidences will be compared between the recipients of Trumenba + MenACWY vaccines and the recipients of MenACWY vaccine.

The exposure cohort will be the individuals who have received at least one dose of Trumenba and at least one dose of MenACWY between 1 January 2016 and 31 December 2021. The non–exposure or reference cohort will be the individuals with no dose of Trumenba but at least one dose of MenACWY vaccine received during the same time period.

PFIZER CONFIDENTIAL CT24-WI-GL03-RF03 2.0 Non-Interventional Statistical Analysis Plan For Secondary Data Collection Study 01-Jun-2020 Page 4 of 28 The date of index vaccination (zero time) for the exposed cohort is the date of the last dose of Trumenba vaccination, after at least one dose of MenACWY. Trumemba and MenAWCY will be identified by Current Procedural Terminology® (CPT) codes and National Drug Codes (NDC) listed in Appendix Tables 4 and 3, respectively. The index date of the unexposed cohort is the first date of MenACWY vaccination. The diseases of interest are gonococcal infection and chlamydia infections occurring at least 14 days after the zero time. International Classification of Diseases, Tenth Revision, Clinical Modification (ICD-10-CM) codes listed in Appendix Table 1 and 2 will identify gonococcal and chlamydia infections, respectively. Only the first episode will be considered as the event in case of repeated infections. Individuals will be followed until the earliest occurrence of the following: outcome, at death date (if known), at plan disenrollment or end of study period.

Study population

This is a retrospective cohort study and the study population are adolescents and young adults approximately 15 to 30 years of age at their date of vaccination (calculated based on birth year) and will be identified from administrative claims during 01 January 2016 and 31 December 2021.

Data source

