4.1 FULL ANALYSIS SET

The full analysis data set will consists of all subjects who met all inclusion/exclusion criteria. Any participant who will not meet the inclusion/exclusion criteria will be excluded from the full analysis set.

Inclusion criteria

 Individuals of approximately 15-30 years old (using July 1 of birth year) enrolled in a health plan available in PharMetrics Plus database during 01 January 2016 and 31 December 2021

PFIZER CONFIDENTIAL CT24-WI-GL03-RF03 2.0 Non-Interventional Statistical Analysis Plan For Secondary Data Collection Study 01-Jun-2020 Page 7 of 28 Individuals having at least one dose of MenACWY during 01 January 2016 and 31 December 2021. MenACWY vaccination will be identified using CPT codes and NDCs listed in Appendix Table 3.

Exclusion criteria

Patients meeting any of the following criteria will not be included in the study:

- Individuals having a dose of Trumemba before their first dose of MenACWY during 01 January 2016 and 31 December 2021
- Individuals having any dose of Bexsero at any time during 01 January 2016 and 31 December 2021. Bexsero vaccination will be identified using CPT codes and NDCs listed in Appendix Table 5.
- 3. Individuals with missing demographic variables or dates of outcome diagnoses or vaccine administration.

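### Two age rules and two reference index dates mean that people first given MenACWY before 15 are filtered differently in the two cohorts

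*SAP*

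**What the plan says.** **Age against the calendar window.** SAP 4 describes the population as "adolescents and young adults 15 to 30 years of age during 01 January 2016" through 31 December 2021. Protocol 9.2.1, repeated in SAP 4.1, admits "Individuals of approximately 15-30 years old (using July 1 of birth year) enrolled in a health plan available in PharMetrics Plus database" in the same window. Neither criterion mentions zero time, and the separate MenACWY criterion sets no minimum age at the dose. SAP 4.1 makes these criteria decisive: "The full analysis data set will consists of all subjects who met all inclusion/exclusion criteria".

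**Age against a dose date.** Protocol 9.1 has people "approximately 15 to 30 years of age at their individual time zero (calculated based on birth year"). The study population paragraph of SAP 2.1 has them "approximately 15 to 30 years of age at their date of vaccination (calculated based on birth year"), without naming the vaccine or the dose.

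**Zero time.** For the reference cohort, protocol 9.1 states: "The index date (zero time) of the reference cohort is the last dose of MenACWY". SAP 2.1 states: "The index date of the unexposed cohort is the first date of MenACWY vaccination". Exposed zero time in SAP 2.1 is "the date of the last dose of Trumenba vaccination, after at least one dose of MenACWY", whatever the age at that earlier MenACWY dose.

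**The 16-23 analysis.** SAP 5.3.2 gives the age range without saying when age is measured.

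**The concern.** Two programmers following the plan faithfully could build different reference cohorts for the primary comparison. The gap matters because exposed follow-up starts at a Trumenba dose, while SAP reference follow-up starts at the first MenACWY dose, which may be several years earlier in life.

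If pre-15 follow-up enters the reference cohort, that cohort carries time outside the age range of the objective. If risk is low at those ages, the reference rate falls and crude VE is biased downward. If such people are instead excluded at their index date, a childhood MenACWY dose removes a person from the reference cohort but not from the exposed cohort. The MenACWY-only comparator was chosen to make the cohorts alike in health seeking and risk behaviour, and a one-sided filter works against that purpose.

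**Working it through.** **1. The plan's own figure.** SAP 3 gives 94% power for 500,000 people, 15% exposed (75,000 against 425,000), event probabilities 0.0036 and 0.0048, HR 0.80 and alpha 0.05 (two-sided, SAP 3.2).
- Expected events: m = 75,000 × 0.0036 + 425,000 × 0.0048 = 2,310.
- Allocation ratio: k = 75,000/425,000 = 0.176.
- Freedman-type formula: power = Φ(√(k·m) × |HR − 1|/(k·HR + 1) − 1.96) = Φ(20.19 × 0.2/1.141 − 1.96) = 94.3%.

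The stated power reproduces. This point does not dispute it.

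**2. The same MenACWY history under each rule.** Take MenACWY at 12 in 2016 and again at 16 in 2020.

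| Rule applied | Never given Trumenba | Trumenba at 16 |
|---|---|---|
| SAP 4/4.1 age rule, first-dose index (SAP 2.1) | In; follow-up starts at 12 | In; indexed at 16 |
| SAP 2.1 age rule taken at the index dose, first-dose index | Dropped (12 at index) | In; indexed at 16 |
| Protocol 9.1 age rule, last-dose index | In; indexed at 16 | In; indexed at 16 |

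The last row is symmetric only because this person was re-dosed at 15 or older. If the only in-window MenACWY dose was at 12, the reference person starts at 12 or is dropped under the last-dose index too, while the Trumenba recipient is kept.

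**3. How much of one person's follow-up can be pre-15.** Assume a first dose on 1 July 2016, on turning 11, 12 or 13. All three turn 15 inside the window and so meet SAP 4 and 4.1. Follow-up to 31 December 2022 (protocol 9.1) is 6.5 years, ignoring the 14-day lag, which changes each share by less than one percentage point. The pre-15 shares are 4/6.5 = 62%, 3/6.5 = 46% and 2/6.5 = 31%. With data ending in October 2022 (SAP 2.1; about 6.25 years) they are 64%, 48% and 32%. These are shares for individuals. The documents do not give the share across the whole reference cohort.

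**4. First reading: effect on crude VE.** Let s be the share of reference person-time before 15, r the pre-15 rate relative to the rate at 15 and older, and assume no pre-15 exposed time. The reference rate is multiplied by 1 − s(1 − r), so

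crude VE = 1 − 0.80/(1 − s(1 − r)) for a true VE of 20%.

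| s (assumed) | r = 0 | r = 0.5 |
|---|---|---|
| 5% | 1 − 0.80/0.95 = 15.8% | 1 − 0.80/0.975 = 17.9% |
| 10% | 1 − 0.80/0.90 = 11.1% | 1 − 0.80/0.95 = 15.8% |
| 25% | 1 − 0.80/0.75 = −6.7% | 1 − 0.80/0.875 = 8.6% |

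**5. Second reading: effect on power.** Removing 10%, 25%, 50% or 75% of the 425,000, with event probabilities held fixed, gives 94.0%, 93.4%, 91.4% or 85.1% by the formula in step 1. Precision is not the main issue. Bias from the one-sided exclusion cannot be calculated from the documents.

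**The case against.** **The age rule is stated.** A reader might infer that the plan never ties age to zero time. That is not so: protocol 9.1 does, and SAP 2.1 ties it to vaccination. SAP 5.4 and Appendix 1 also calculate age at a vaccination date, and Table 1.1 lists age at vaccination in groups starting at 15-17, so a reference person indexed at 12 would have no row. This stands, and it makes exclusion the likelier reading and pre-15 follow-up the less likely one. It does not settle the matter, because SAP 4.1 defines the full analysis set by criteria that lack the anchor. Likewise, Table 1.2 points to age at vaccination for the 16-23 analysis, but names no dose.

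**The primary VE is adjusted for age.** A reader might infer from step 4 that the primary estimate could turn negative. The documents do not support that: those figures are crude and rest on assumed shares and rates. A baseline-age category under 15 containing only reference people would contribute almost nothing to the vaccine coefficient, so the bias would largely disappear. But the SAP does not state the functional form of age, its table groups have no under-15 category, and a single linear term would have to extrapolate where there are few or no exposed people.

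**Pre-15 time need not fall in the reference cohort alone.** Under SAP 4 and 4.1 read literally, Trumenba given before 15 could bring pre-15 time into the exposed cohort too. This is correct, and step 4 is conditional on there being none.

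**The protocol's last-dose index keeps the example person.** This is also correct, so the conflict over the index dose is part of the cause. As step 2 shows, it helps only those re-dosed at 15 or older.

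**Conclusion.** The documents contain two age rules and two reference index dates, and these need to be reconciled. With the SAP's first-dose index, people first given MenACWY before 15 are handled differently by cohort under either age rule.

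- **SAP 4/4.1 read literally:** crude VE is biased downward if pre-15 risk is low. For a true VE of 20%, with 5-10% of reference person-time before 15 at 0 to 0.5 times the later rate, it would read about 11-18%. Both the share and the rate ratio are assumptions. Age adjustment would reduce the bias, and would remove it fully only if age is modelled flexibly with an under-15 category.
- **SAP 2.1 (likelier):** the problem is comparability of the cohorts. Neither direction nor size can be derived from the documents, and it is not mainly a power problem.

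This should be settled before the cohort program is run, because it determines who enters the primary comparison.

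**What to change.** 1. Write *aged 15-30 years at zero time*, for both cohorts, in protocol 9.2.1, SAP 2.1, SAP 4 and SAP 4.1, and *16-23 years at zero time* in SAP 5.3.2.
2. Reconcile the first-dose and last-dose index between protocol 9.1 and SAP 2.1.
3. Choose the reference index dose only among in-window MenACWY doses given at age 15-30, so that an earlier childhood dose neither starts follow-up nor removes the person.
4. Apply the same requirement, an in-window MenACWY dose at age 15-30, to the exposed cohort, at least as a sensitivity analysis. Without this the asymmetry remains: a person with one MenACWY dose at 12 and Trumenba at 16 stays exposed, while the counterpart with only the childhood dose is dropped.

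The cost is wording in these sections, one filter in the cohort program, and some records removed or moved to a later start. The documents do not give their number. No new data are needed.

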4.1 FULL ANALYSIS SET

The full analysis data set will consists of all subjects who met all inclusion/exclusion criteria. Any participant who will not meet the inclusion/exclusion criteria will be excluded from the full analysis set.

Inclusion criteria

 Individuals of approximately 15-30 years old (using July 1 of birth year) enrolled in a health plan available in PharMetrics Plus database during 01 January 2016 and 31 December 2021

PFIZER CONFIDENTIAL CT24-WI-GL03-RF03 2.0 Non-Interventional Statistical Analysis Plan For Secondary Data Collection Study 01-Jun-2020 Page 7 of 28 Individuals having at least one dose of MenACWY during 01 January 2016 and 31 December 2021. MenACWY vaccination will be identified using CPT codes and NDCs listed in Appendix Table 3.

Exclusion criteria

Patients meeting any of the following criteria will not be included in the study:

- Individuals having a dose of Trumemba before their first dose of MenACWY during 01 January 2016 and 31 December 2021
- Individuals having any dose of Bexsero at any time during 01 January 2016 and 31 December 2021. Bexsero vaccination will be identified using CPT codes and NDCs listed in Appendix Table 5.
- 3. Individuals with missing demographic variables or dates of outcome diagnoses or vaccine administration.

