9.2. Setting

IQVIA PharMetrics[®] Plus is a longitudinal health plan database of adjudicated medical and pharmacy claims, including patient enrollment data for national and sub-national health plans and self-insured employer groups in the US. Administrative claims and enrollment data available during 01 January 2016 and 31 December 2022 will be used in this study.

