9.2.2. Exclusion Criteria

Patients meeting any of the following criteria will not be included in the study:

Individuals having any dose of Bexsero at any time during 01 January 2016 and 31 December 2021 and prior to the study

Individuals with missing demographic variables or dates of outcome diagnoses or vaccine administration (listed in Section 9.3).

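### The Bexsero exclusion acts on doses given after follow-up has started, while doses in 2022 are neither excluded nor censored

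*SAP*

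**What the plan says.** The SAP (4.1) excludes "Individuals having any dose of Bexsero at any time during 01 January 2016 and 31 December 2021". The protocol (9.2.2) words it as "Individuals having any dose of Bexsero at any time during 01 January 2016 and 31 December 2021 and prior to the study". Its extra clause reaches back before the study; it does not limit the rule to doses before the person's own zero time, and it does not extend the rule into 2022.

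Zero time is a vaccination date within 2016-2021. In SAP 2.1 it is, for the exposed cohort, "the date of the last dose of Trumenba vaccination, after at least one dose of MenACWY". For the reference cohort: "The index date of the unexposed cohort is the first date of MenACWY vaccination". (Protocol 9.1 uses the last MenACWY dose for the reference cohort. That conflict changes how much follow-up precedes the end of 2021, but not the point made here.) Follow-up for the outcome starts 14 days after zero time.

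Follow-up continues past the Bexsero window. Protocol 9.2 states: "Administrative claims and enrollment data available during 01 January 2016 and 31 December 2022 will be used in this study", and protocol 9.1 and 9.7 end the study on 31 December 2022. SAP 2.1 gives October 2022 as the latest data release.

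The censoring lists in protocol 9.1 and 9.7 and in SAP 2.1, 5.1.1, 5.3 and 7.2.1.1 name, in varying combinations, the outcome, death, disenrollment and the end of the period. None names Bexsero.

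**The concern.** Eligibility for a cohort should be decided from what is known when follow-up starts. Here a person indexed in 2017 who takes Bexsero in 2021 is removed altogether, including about four years of valid follow-up and any infection in that time. The same dose in January 2022 has no effect on the analysis. Neither document explains the difference.

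The removal is unlikely to be even across cohorts. Someone who already has Trumenba has little reason to take the other MenB vaccine, so later Bexsero probably removes mainly reference people. The protocol chose a MenACWY-only reference "in order to help control for theoretical differences in health seeking and risk behaviors between vaccinated and unvaccinated individuals", and removing those who later seek a MenB vaccine works against that aim. Adjustment for age, sex and US region cannot be expected to restore the difference.

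Bexsero time in 2022 is not neutral either: protocol section 7 reports effectiveness of that vaccine against gonorrhoea of 26% for one dose and 40% for the full course.

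**Working it through.** **The plan's own figure.** The point disputes no stated number, but the cost of a change depends on power, so I reproduced the SAP section 3 figure first. Inputs: 500,000 people, 15% exposed (75,000 against 425,000), failure probabilities 0.0036 and 0.0048, HR 0.80, two-sided alpha 0.05.

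- Events: 75,000 × 0.0036 + 425,000 × 0.0048 = 270 + 2,040 = 2,310.
- k = 75,000/425,000 = 0.1765.
- Power = Φ(√(k × 2,310) × 0.20/(0.80k + 1) − 1.96) = 94.3%, against 94% stated. It reproduces.

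**Exclusion on a later dose.** The documents give no count, timing or risk for later Bexsero takers, so the inputs are assumptions. Let a share q of the reference cohort, and nobody in the exposed cohort, be removed. Let the hazard of those removed be r times that of the rest. The full reference cohort has a hazard proportional to (1 − q) + qr, and after removal it is 1. Hence

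observed HR = true HR × [(1 − q) + qr].

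| q | r | true VE 20% reads | true VE 0% reads |
|---|---|---|---|
| 2% | 0.5 | 20.8% | 1% |
| 2% | 2 | 18.4% | −2% |
| 10% | 0.5 | 1 − 0.8 × 0.95 = 24% | 5% |
| 10% | 1 | 20% | 0% |
| 10% | 2 | 1 − 0.8 × 1.10 = 12% | −10% |

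The sign depends entirely on whether r is below or above 1.

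**Doses in 2022.** If a fraction f of reference person-time follows a 2022 dose with effectiveness e, observed HR = true HR/(1 − ef). With e = 40%:

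- f = 0.5%: 1 − 0.8/0.998 = 19.8%.
- f = 1.25%: 1 − 0.8/0.995 = 19.6%.
- f = 5%, an extreme: 1 − 0.8/0.98 = 18.4%.

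With e = 26% and f = 0.5% the result is 19.9%. The shift is toward the null provided the doses fall mainly in the reference cohort.

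**What censoring at the dose recovers.** Suppose takers contribute a fraction g of full follow-up before the dose (assumed 25-50%). Their share of reference person-time is then w = qg/(1 − q + qg). For q = 10% this is 0.025/0.925 = 2.7% to 0.05/0.95 = 5.3%. The reference hazard becomes 1 − w + wr.

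- r = 2: HR = 0.88/1.027 to 0.88/1.053, so VE reads 14.3% to 16.4% instead of 12%.
- r = 0.5: HR = 0.76/0.986 to 0.76/0.974, so VE reads 23.0% to 21.9% instead of 24%.

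Censoring moves the estimate toward 20% in both cases but does not reach it, because takers still leave the reference cohort at the dose.

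**Power after the change.** Assume 1-10% of the 500,000 are restored with 25-50% of their follow-up. Events rise to 2,316-2,430; the upper figure is 2,310 + 50,000 × 0.5 × 0.0048. The same formula gives 93-95%. The slight fall at the low end arises because the formula counts restored people in the allocation ratio as if fully followed; no information is lost.

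**The case against.** Several counterarguments have weight.

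The intended contrast is Trumenba plus MenACWY against MenACWY alone, in a study that calls itself exploratory, and removing Bexsero recipients serves that contrast. The aim is sound, but censoring at the dose serves it too without using future information.

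Protocol 9.9 uses chlamydia as a reference outcome, and a hazard ratio below 1 there is to be taken as residual confounding. The same exclusion applies to that analysis, so a distortion of health-seeking behaviour might show up. It can signal the problem; it does not repair it.

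Censoring has its own weakness. If later takers are mainly reference people with a different risk, censoring them is differential and possibly informative, as the partial recovery above shows. This stands and belongs among the costs.

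A reader might infer something stronger: that the rule inflates VE because vaccine seekers have lower risk. If people who seek a MenB vaccine have RR times the risk of others and Trumenba does nothing, the HR reads RR under the exclusion and RR/(1 − w(1 − RR)) with pre-Bexsero time kept. RR 0.9 with w 5% gives 0.9/0.995 = 0.905, half a point of VE. RR 0.7 with w 15% gives 0.7/0.955 = 0.733, or 26.7% instead of 30%, a gap of 3.3 points. The documents do not support this as a finding. They say nothing about the risk of later takers, and a higher risk reverses the sign. The upper end also needs q = 0.15/(0.15 + 0.85g), or 26% (g = 50%) to 41% (g = 25%) of the reference cohort taking Bexsero after index. Protocol section 7 puts coverage of any MenB vaccine at 32% in 2021, though in a different population. Even on those assumptions 26.7/30 = 89% of the spurious effect would remain after the change, because it comes from general confounding between the cohorts.

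**Conclusion.** The defect holds on the text. A Bexsero dose up to 31 December 2021 removes a person even when it follows the start of follow-up, a 2022 dose is ignored, and nothing is censored at the dose. That discards valid person-time and events and makes eligibility depend on the future.

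The direction and size of the resulting bias cannot be determined from the documents. The 24% to 12% range rests on two assumptions: 10% of the reference cohort removed with none from the exposed cohort, and a relative hazard of 0.5 to 2. That the removal falls mainly on the reference cohort is plausible but not shown. The 2022 gap amounts to tenths of a point under the 0.5-1.25% assumption and would not justify a change by itself.

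The change is worth making because it is cheap and removes a selection whose direction cannot be predicted. It does not make the cohorts comparable in general, and it leaves untouched the separate requirement in protocol 9.1 that reference members receive no Trumenba throughout observation, which also looks forward.

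**What to change.** - In SAP 4.1 and protocol 9.2.2, exclude only people with a Bexsero dose on or before the start of follow-up, including any recorded dose before the study. Use the same wording in both documents.
- In both cohorts, add the first later Bexsero dose to every censoring list, using doses through the end of follow-up. Reconcile the two end dates (31 December 2022 and October 2022) first.
- Keep the current exclusion as a sensitivity analysis.
- Report the number censored at Bexsero by cohort, and add an analysis without that censoring.

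Cost: one eligibility sentence, one censoring date and a little programming. The Bexsero codes are already listed (SAP Appendix 3, Table 5) and the protocol's claims period covers 2022. Power stays at about 93-95% under the assumptions above. The real downside is that censoring at Bexsero may be informative and may differ between cohorts, which is why the last item is needed.
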